In Aim 3, we will conduct a randomized controlled trial among 50 patients with heart failure. Twenty-five patients (n=25) will be randomized to the digitally-enabled CHW intervention + usual care (explored in Aim 2) and 25 patients will be randomized to CHW care + usual care. Outcomes will include patient acceptability (defined by patient satisfaction, willingness to engage in the intervention again, etc.), feasibility (rate of patient biosensor, mobile application, symptom assessment, Everion sensor, digital blood pressure monitor, digital weight scale, and CHW interaction use) and preliminary effectiveness (30-day readmissions, ED visits, missed primary care and cardiology appointments). CHW exit interviews (15-minute) will also be conducted after each patient study interval ends. The hypothesis is that a 30-day digitally-enabled CHW intervention can generate high acceptability, feasibility, and preliminary effectiveness among patients with heart failure.

Aim1

Identification of 30 patient and 20 community health worker perspectives on barriers to heart failure care through semi-structured interviews and focus groups

Outcomes: The domains of the interview and focus group guides: HF knowledge, social (e.g., socioeconomic status, social support, living situations), behavioral (e.g., diet, activity), clinical (e.g., medication reconciliation, care plan adherence), communication-based (e.g., connection to care teams), digital (e.g., medication reminders, appointment reminders), human (e.g., CHW home visits, accompaniment to clinic visits), disease-based (e.g., HF and other comorbidities), cultural (e.g., health beliefs), or environmental (e.g., work, home) factors

Hypothesis: Interviews with patients with HF and CHW focus groups can improve a HF intervention

Aim 2

Conduct a 30-day open pilot trial with 30 patients (10 patients at a time for 3 consecutive cycles) at hospital discharge by orienting patients to the use of the digital platform and pairing patients with community health workers trained to use the digital platform and care for patients with heart failure.

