For intervention participants, at the time of enrollment, participants will be instructed on use of the Biofourmis mobile application with the aid of a study coordinator. All enrolled participants will also be given and taught how to use a Bluetooth enabled digital blood pressure monitor (for blood pressure monitoring each day), digital weight scale (for body weight monitoring each day) as well as a Everion biosensor with associated arm band (used to monitor and heart rates, oxygenation, activity levels, etc). Participants will wear the arm band every day for 30 days; they will also take their blood pressure, weigh themselves with the digital blood pressure monitor and weight scale monitor, respectively, at least once a day. Participants will also be encouraged to view educational videos within the Biofourmis application about heart failure and wellness.

While the Biofourmis application can be downloaded by anyone, the application may only be used by those that have a profile/access code for the application. All enrolled participants are expected to complete all questionnaires associated with the study and return the loaned Everion and digital blood pressure and weight scale at the study end. Data collected during the study will reside in secured data settings (all data generated from Biofourmis app use/ digital blood pressure monitor/digital weight scale/Biofourmis armband) or REDCap (questionnaire responses).

Inclusion/Exclusion Criteria

Eligibility amongst adult patients admitted who meet all eligibility criteria will be considered. The following inclusion criteria will be applied. Patients must:

- 22) be between the ages of 18-95
- 23) have a diagnosis of heart failure
- 24) admitted to MGH within 24 months of the time of enrollment

- 25) own a smart phone and be familiar with common user features
- 26) live within a 35-mile radius of MGH ([name])
- 27) have a working home/mobile telephone number where they can be reached
- 28) be English speaking
- 29) able to consent to study participation
- 30) have a primary care provider
- 31) have unmet needs for outpatient support identified during screening for study enrollment (e.g., assistance with medication management, appointment scheduling, transportation, social support)

The following exclusion criteria will be applied. Exclusion will apply to patients that:

- 9) are homeless at the time of admission

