A randomized controlled trial will be performed of the 30-day intervention among 50 patients with HF randomized to the intervention arm (digitally-enabled CHW + usual care) or the control arm (CHW care + usual care). Participants randomized to the intervention arm will be enrolled(n=25) and participants will receive the 30-day digitally-enabled CHW intervention (usual care + digitally-enabled CHW care). Participants randomized to the control arm will be enrolled (n=25) and participants will receive the 30-day CHW intervention (usual care with CHW care). A chart review will also be completed for all participants. All patient participants will also complete 10-minute exit interviews with completion of a questionnaire in person or via phone at study day 25 and at the end of the 30-day interval. CHWs will also complete an exit interview at the end of each 30-day study interval pairing.

Eligible inpatients will be identified through a number of different ways. Inpatients presenting with congestive heart failure exacerbation as the primary diagnosis and hospitalized on a relevant MGH inpatient units and meeting all eligibility criteria will be recruited. All study criteria will be confirmed with patients directly and an informational letter introducing the study purpose and payment for participation (\$250 per patient) will be given to eligible patients. After agreeing to the study and providing written informed consent, patients meeting study criteria will be enrolled and CHW staff will meet and establish patient- centered goals for the study interval prior to hospital discharge. Patients unable to be fully enrolled and given study equipment prior to discharge will be contacted via phone and if interested have the option of returning to MGH at a convenient time.

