Study coordinator approaching patients will present an informational letter introducing the qualitative study aim purpose and payment for participation (\$50 per patient) will be given to eligible patients. Interested patients will be verbally consented and interviewed at the bedside or via phone (25 min).

Community Health Workers

CHWs interested in participating will be enrolled and scheduled for a focus group (1.5 hours) at MGH ([name]), via virtual meeting accessed via MGB generated Zoom link, or at 1-2 MGH community clinics. Payment for participation will be \$50 per CHW.

Aim 2

Patients

Patients with heart failure and meeting all eligibility criteria will be recruited. All study criteria will be confirmed with patients directly and an informational letter introducing the study purpose and payment for participation (\$250 per patient) will be given to eligible patients. After agreeing to the study and providing written informed consent, patients meeting study criteria will be enrolled and CHW staff will meet and establish patient- centered goals for the study interval.

The Biofourmis mobile application, Biofourmis arm band, digital blood pressure monitor, and digital weight scale will be provided at no cost to the participant for the duration of the study. Participants will be able to keep the Biofourmis mobile app access but will need to return the blood pressure monitor, weight scale, and Everion arm band following study completion.

No additional hospital visits or out of pocket expenses related to study participation will be incurred.

Community Health Workers

CHWs for this study aim will be paid study staff and no remuneration for study aim participation will be given.

Aim 3

Patients

Patients with heart failure and meeting all eligibility criteria will be recruited. All study criteria will be confirmed with patients directly and an informational letter introducing the study purpose and payment for participation (\$250 per patient randomized to intervention or control) will be given to eligible patients. After agreeing to the study and providing written informed consent, patients meeting study criteria will be enrolled and randomized (block randomization, blocks of 3) to intervention or control. CHW staff will meet and establish patient- centered goals for the study interval at the time of enrollment.

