For Aim 3, data analysis will include the following: Summary statistics for the acceptability and feasibility of the intervention will be reported with 95% confidence interval. For effectiveness of the intervention, the proportion with 30-day readmissions or missed appointments will be compared using Pearson's χ^2 tests and the number of ED visits will be compared using a Poisson model. Other variables in the post-study questionnaires will be compared between the two groups in a separate analysis. The relationship between potential predictors and outcomes will be explored. In [name] prior CHW clinical trial, <3% of patients were lost to follow-up and similar rates are expected here. REDCap activity log and patient use assessments will also be summarized.

For Aim 3, power calculations will be based on a sample $n=50$. The study will have a minimum of 83% power to detect a 40% difference between the two groups with a two-sided significant level of 0.05. As a pilot study, the sample size is not powered to detect small differences between the two groups. However, the study will provide estimates for the effect size which can be used in the future R01 study.

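### Aim 3 pools current heart failure inpatients with outpatients last admitted up to 24 months ago, but names recruitment setting neither as a stratification factor nor as a covariate; including it would give a cheap, modest gain in precision and balance.

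*Combined protocol and SAP*

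**What the plan says.** Under Specific Aims: "In Aim 3, we will conduct a randomized controlled trial among 50 patients with heart failure". Half go to the digital arm ("Twenty-five patients (n=25) will be randomized to the digitally-enabled CHW intervention + usual care") and half to CHW care with usual care.

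Two kinds of patient can enter. The Aim 3 study procedures recruit "Inpatients presenting with congestive heart failure exacerbation as the primary diagnosis". The same section, and the Aim 3 recruitment text, also allow portal letters and announcements, mail, and referral from primary care or cardiology. For those patients the Aim 3 inclusion list asks only that they were "admitted to MGH within 24 months of the time of enrollment", with no cause of admission specified.

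The allocation rule appears once, in the Aim 3 remuneration text under Recruitment Procedures: "patients meeting study criteria will be enrolled and randomized (block randomization, blocks of 3) to intervention or control". The documents are silent on stratification; they neither plan it nor rule it out.

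Section 4.4 compares 30-day readmissions and missed appointments with Pearson's chi-square test and ED visits with a Poisson model. It names no covariates for these comparisons and leaves predictors of outcome to exploration. It describes the trial as a pilot that should supply effect-size estimates for a later R01 study.

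**The concern.** The two groups are at different points in the disease course. An inpatient recruit is usually followed soon after an exacerbation admission. A portal or mail recruit may be followed nearly two years after an admission for any cause. It is plausible that the first group has the higher 30-day admission risk, and which group a patient belongs to is known before allocation.

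If chance gives one arm more inpatients, the crude difference in readmissions carries part of that imbalance, and nothing in the specified analysis removes it. What is at stake is the effect estimate to be taken forward to the R01. That estimate would be somewhat noisier than it need be and, in a given realised trial, shifted in a direction that the pooled analysis does not show.

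**Working it through.** **Inputs from the documents.** 50 patients, 25 per arm; "two-sided significant level of 0.05"; unadjusted chi-square test; no stratification factor.

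**Inputs assumed, because the documents do not give them.** Inpatients K = 10 to 30 of 50. 30-day admission risk of 25% (inpatient) against 5% (outpatient), with 30% against 2% as a wider gap and 20% against 10% as a narrower one.

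**Step 1: the plan's own figure.** Section 4.4 states: "The study will have a minimum of 83% power to detect a 40% difference between the two groups". Reading this as 40 percentage points, power is lowest at 0.70 against 0.30:
- SE under the null = √(2 × 0.5 × 0.5 / 25) = 0.1414
- SE under the alternative = √((0.21 + 0.21) / 25) = 0.1296
- Power = Φ((0.40 − 1.96 × 0.1414) / 0.1296) = Φ(0.95) = 82.8%

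This agrees with the stated 83%, so the design difference against which to judge any shift is 40 points.

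**Step 2: chance imbalance.** Let X be the number of inpatients in one arm. If allocation ignores setting and the arms hold 25 each, X is hypergeometric (50, K, 25). The arm difference is D = 2X − K. The average shift in the readmission difference is E|D| / 25 × (risk gap).

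| K | P(abs D ≥ 5) | P(abs D ≥ 7) | E abs D | Average shift, 25% vs 5% | Average shift, 30% vs 2% |
|---|---|---|---|---|---|
| 10 | 7% | 1% | 2.20 | 1.8 points | 2.5 points |
| 15 | 22% | 6% | 2.66 | 2.1 | 3.0 |
| 20 | 15% | 4% | 2.72 | 2.2 | 3.0 |
| 25 | 26% | 9% | 2.89 | 2.3 | 3.2 |
| 30 | 15% | 4% | 2.72 | 2.2 | 3.0 |

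Odd K gives the larger tail probabilities because an even K cannot produce a difference of exactly 5 or 7.

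Blocks of 3 that ignore setting change this little. With K = 25 and blocks assumed to alternate at random between 2:1 and 1:2, the inpatient share differed by at least 20 points (5 of 25) in about 21% of simulated lists and by at least 28 points (7 of 25) in about 7%.

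**Step 3: shift at a 7-patient imbalance.**
- 25% vs 5%: 7/25 × 0.20 = 5.6 points
- 30% vs 2%: 7/25 × 0.28 = 7.8 points
- 20% vs 10%: 7/25 × 0.10 = 2.8 points

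**Step 4: comparison with sampling error, K = 25.** With exact balance the variance of the difference is 2 × [½r₁(1−r₁) + ½r₂(1−r₂)] / 25. Without stratification, add (SD of the share difference × risk gap)², where the SD of the share difference is 0.143.
- 25% vs 5%: balanced √0.0094 = 9.7 points; unstratified √(0.0094 + 0.0286²) = 10.1 points
- 30% vs 2%: balanced √0.00918 = 9.6 points; unstratified √(0.00918 + 0.0400²) = 10.4 points

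The unstratified 95% CI half-width is about 1.96 × 10.1 to 1.96 × 10.4, or about 20 points.

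**Step 5: type I error.** In 100,000 simulated null trials (K = 25, 25% vs 5%), the chi-square test rejected in 5.4% unstratified and 4.7% stratified. Among unstratified trials with at least 20 points of imbalance in inpatient share, it rejected in 6.9%. With 30% vs 5% the three figures are 5.5%, 4.2% and 7.8%.

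**The case against.** The strongest reply is that stratification is optional. Randomisation makes the comparison valid whether or not setting is balanced, and at n = 50 the estimate is imprecise mainly because the trial is small. A standard error falling from 10.1 to 9.7 points hardly changes what the pilot can say. Aim 3 is also about acceptability and feasibility, and device use in the intervention arm does not depend on balance between arms. Section 4.4 states that the trial is not powered for small differences, and it leaves room to explore predictors.

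Most of this stands, and it limits the claim. A reader might infer that the readmission, ED and appointment results would reflect the patient mix as much as the platform, or that the effect estimate would be unreliable for this reason. The figures do not support that: the average shift is about a tenth to a sixth of the CI half-width, and even 7.8 points is far from the 40-point design difference. A reader might also take setting to be the strongest available predictor. The documents give no risk by setting, and all Aim 3 patients must have unmet outpatient support needs, which may narrow the gap. With 20% against 10%, the average shift at K = 25 is only 2.89/25 × 0.10 = 1.2 points.

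What the reply does not remove is that the planned exploration of predictors is unspecified, so it does not commit the team to an adjusted estimate. The remedy is also almost free.

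**Conclusion.** The point holds as a low-cost improvement, not as a flaw in the validity of the trial. Aim 3 combines two recruitment settings that plausibly differ in 30-day risk, and neither the allocation nor the specified analysis uses that information.

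Under the assumed inpatient shares (10 to 30 of 50), a difference of 5 or more inpatients between arms has a 7-26% chance and of 7 or more a 1-9% chance. Under the two wider risk gaps the readmission difference shifts by about 2-3 points on average and by 5.6-7.8 points at a 7-patient imbalance. Balancing on setting lowers the standard error by about 4-8% with 25 inpatients and reduces conditional bias in the estimate meant for the R01. All of these sizes depend on the assumed shares and risks; a narrower true gap makes them smaller.

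**What to change.** **Allocation** (Aim 3 remuneration text, with matching wording in the Aim 3 study procedures and Aim 3 recruitment text). Stratify by how the patient was identified: during a current heart failure admission, or as an outpatient by portal, mail or referral. State that patients identified in hospital who complete enrolment after discharge belong to the first stratum. Use an even block size, because a block of 3 cannot split equally between two arms.

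**Analysis** (section 4.4). Use the same factor: a Mantel-Haenszel risk difference for readmission and missed appointments, and setting as a covariate in the Poisson model for ED visits. Show the effectiveness outcomes descriptively by setting, so that the R01 team can see which patients the estimate describes.

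**If allocation has already begun**, leave it and prespecify the setting-adjusted analysis alone.

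**Cost.** One extra randomisation list and one extra table. With two lists there can be two incomplete final blocks, so arm totals may differ by a patient or two.

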4.4 Statistical Design and Power

1. Statistical Analysis

For Aim 1, transcription and interviewer/moderator notes will be uploaded into NVivo 10 for analysis. [name] and a research coordinator will first independently code patient data followed by CHW focus group data. The framework used will include an approach where two researchers will familiarize themselves with the raw data, independently identify key themes raised by respondents, and reapply this thematic framework by rearranging the raw data into themes and relationships. Associations between themes, user characteristics, and outcomes will be identified. Each coder will perform content analysis to capture themes associated with each focus group and patient interview. These will be compared by gender and age. Intercoder reliability will be achieved through an iterative process of comparing each level of coding (themes and codes) while discussing discrepancies and comparing results to the raw data until $\text{Kappa} > 0.80$ is achieved. Themes will be reviewed and discrepancies discussed with a third researcher, [name], with expertise in qualitative data. [name] will also perform an expert review of the data analysis and interpretation. [name] will review patient transcripts weekly with interviewer staff to discuss emerging themes, modify the patient interview instrument as needed, and assess for theoretical saturation. If necessary, [name] will make modifications to the patient interview instrument to increase the contextual relevance. Due to the small number of focus groups used ($n=2$), no modifications will be made to the CHW focus group instrument after the first focus group occurs.

For Aim 2, interview transcriptions and interviewer notes will be reviewed weekly by [name] and themes will be categorized as described above in Aim 1 and in the Research Strategy section E.7. These themes will be used to refine the intervention prior to each new iteration (maximum of 3 study runs) informing the RCT intervention in Aim 3. [name] review of the REDCap core competency/activity log checklists and digital platform patient use data will also inform intervention refinement.

For Aim 3, data analysis will include the following: Summary statistics for the acceptability and feasibility of the intervention will be reported with 95% confidence interval. For effectiveness of the intervention, the proportion with 30-day readmissions or missed appointments will be compared using Pearson's χ^2 tests and the number of ED visits will be compared using a Poisson model. Other variables in the post-study questionnaires will be compared between the two groups in a separate analysis. The relationship between potential predictors and outcomes will be explored. In [name] prior CHW clinical trial, <3% of patients were lost to follow-up and similar rates are expected here. REDCap activity log and patient use assessments will also be summarized.

For Aim 3, power calculations will be based on a sample $n=50$. The study will have a minimum of 83% power to detect a 40% difference between the two groups with a two-sided significant level of 0.05. As a pilot study, the sample size is not powered to detect small differences between the two groups. However, the study will provide estimates for the effect size which can be used in the future R01 study.

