Outcomes: Digital CHW intervention usability: the usability outcome will be defined by facilitators and barriers to platform use (the ability to implement the intervention, enroll patients, and collect data). These data will be collected via qualitative interviews with patients and CHW staff participating in the open pilot trial. Rates of Everion biosensor, phone application, symptom assessment, frequency of CHW in-person or phone interactions, total and proportional patient time spent engaged with the digital platform (e.g., time spent with the arm biosensor in place, frequency of blood pressure monitor use, and frequency of digital platform video interactions per day) will also be tracked.

Hypothesis: Use of qualitative data (collected during patient and CHW interviews), along with usability data in an open pilot trial can inform intervention design refinement for a digitally-enabled CHW in a clinical trial.

Aim 3:

Conduct a 30-day randomized controlled trial with HF patients randomized to either the digitally-enabled CHW intervention + usual care (n=25) or to CHW care + usual care (n=25).

Outcomes: Outcomes will include patient acceptability (defined by patient satisfaction, willingness to engage in the intervention again, etc.), feasibility (rate of patient biosensor, mobile application, symptom assessment, Everion sensor, digital blood pressure monitor, digital weight scale, and CHW interaction use) and preliminary effectiveness (30-day readmissions, ED visits, missed PC and cardiology appointments). CHW exit interviews (15-minute) will also be conducted after each patient study interval ends.

Hypothesis: A 30-day digitally-enabled CHW intervention can generate high acceptability, feasibility, and preliminary effectiveness for patients with HF.

BACKGROUND AND SIGNIFICANCE

Provide a brief paragraph summarizing prior experience important for understanding the proposed study and procedures.

There were approximately 3.3 million adult 30-day all-cause hospital readmissions in the USA, generating \$41.3 billion in hospital costs.¹ Up to 20% of these readmissions or \$8.26 billion in health care expenditures were potentially

preventable.² Reasons for preventable readmission are multifactorial and associated with disease conditions, age, and healthcare utilization.^{3,4}

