Patients with congestive heart failure are the leading population of patients readmitted within thirty days of a previous hospitalization.⁵ Ongoing efforts to reduce readmission rates for heart failure patients have included public reporting and readmission penalties instituted by the Centers for Medicare & Medicaid Services (CMS) as well as numerous national campaigns focused on supporting programming to assist hospitals in this effort.^{6,7,8} Despite AHA goals to reduce readmissions by 20% by 2016, the goal has yet to be achieved.⁹

Community Healthcare Worker (CHW) care delivery is one of very few health interventions demonstrated to reduce health care utilization among populations with chronic disease.¹⁰ As embedded members of healthcare teams, CHWs function as expert coaches voiced in motivational interviewing and goal-setting. CHWs also call/visit patients or even show up outside patient homes in a hired car to take them to medical appointments. Despite noted improvement in healthcare outcomes by as much as 18-65% with the use of CHW interventions,¹¹ studies exemplifying that CHW models can improve specific outcomes targeted by the Centers for Medicare and Medicaid (i.e. 30-day readmission rates) have been scant and no studies have been completed examining a digitally-enabled CHW intervention for patients with heart failure. Data analysis performed on 550 patients enrolled in a small randomized controlled trial, pairing patients at high risk for readmission with CHWs, indicated that intervention study participants as compared to controls had 40% lower 30-day readmission rates, 20% less emergency room visits, 30% less missed post-discharge appointments.¹⁴ Thirty-three percent of these enrolled participants had a diagnosis of heart failure.

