- 10) do not have cognition to complete the survey or require caregiver prompting or response for questionnaire completion
- 11) have a history of known lack of capacity to consent (due to guardianship or invoked health care proxy)
- 12) visual, motor or hearing deficits that precludes engagement with the intervention.

For Aim 3, each participant will join the study following enrollment for a typical study duration of approximately 30 days.

The Aim 3 sample size is defined as the maximum number of people that we can enroll with the equipment resources available as well as the minimum number of individuals that would be required to demonstrate value or statistical significance in terms of preliminary effectiveness.

Briefly describe study procedures. Include any local site restrictions, for example, "Subjects enrolled at Partners will not participate in the pharmacokinetic portion of the study." Describe study endpoints.

Aim 1

Patients

Patients with heart failure that are hospitalized may be approached, introduced to the Aim 1 study and verbally consented in the hospital prior to the administering the interview guide via phone after patients return home after hospital discharge. Also, patients eligible for Aim 1 enrollment may also be identified from a pool of 62 heart failure respondents from a previous randomized controlled trial (PI, [name]; Protocol #2016P002768) who agreed to be contacted for future additional research activities. These patients may be contacted by phone and introduced to study Aim 1. All study criteria will be confirmed with patients directly and an informational letter introducing the qualitative study purpose and payment for participation (\$50 per patient) will be given to eligible patients (via email or snail mail). If interested, patients will be able to review the informed consent document. All questions will be answered about all aspects of the study listed on the

information sheet and the informed consent document. If interested in enrolling in the study, patients will then give verbal consent and be interviewed by a study coordinator via phone (25 min). All patient interviews will be audio recorded and transcribed verbatim. Dedoose will be used to analyze themes generated by the interviews. A chart review for readmitted study participants will also be performed by study staff. A REDCap database will be used to store all questionnaire and chart review data.

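### The 83% power figure holds only for an absolute 40-point gap with near-equal arms; it does not show that n=50 suffices for significance on the prior trial's effects, and blocks of 3 conflict with 25/25

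*Combined protocol and SAP*

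**What the plan says.** - **Power (4.4 Statistical Design and Power).** With n=50 and a two-sided 0.05 level, Aim 3 has a "minimum of 83% power to detect a 40% difference between the two groups". The sentence does not say whether the difference is absolute or relative, which endpoint it concerns, or what control rate is assumed. The section adds that, as a pilot, the study is not powered for small differences and will supply effect-size estimates for a later R01.
- **Planned tests (same section).** Readmission and missed appointments are compared by Pearson chi-square, and ED visit counts by a Poisson model.
- **Sample size (Research Design and Methods, Aim 3).** The number is called the most the equipment allows, and also "the minimum number of individuals that would be required to demonstrate value or statistical significance in terms of preliminary effectiveness". Specific Aims spells out the domain: "preliminary effectiveness (30-day readmissions, ED visits, missed primary care and cardiology appointments".
- **Prior effects (Background and Significance).** An earlier trial of CHW care against controls is reported as showing "40% lower 30-day readmission rates, 20% less emergency room visits, 30% less missed post-discharge appointments". The same paragraph mentions an 18-65% improvement in unnamed healthcare outcomes with CHW interventions.
- **Arms (Specific Aims and elsewhere).** Twenty-five go to the digital arm and "25 patients will be randomized to CHW care + usual care".
- **Randomization (Recruitment Procedures, remuneration, Aim 3).** Patients are "randomized (block randomization, blocks of 3) to intervention or control". No within-block ratio is given.

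**The concern.** The figure 40% appears twice with different meanings. In the Background it is the prior trial's readmission result. In Section 4.4 it is the difference the trial is powered for. A reader who also meets the sample-size sentence may conclude that 50 patients give 83% power for an effect like the earlier one. If Section 4.4 means percentage points, that conclusion is wrong, and a non-significant Aim 3 result could be carried into the R01 as a well-powered null.

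The stated minimum also presupposes roughly equal arms, and the block rule does not secure them.

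**Working it through.** **Inputs.** From the documents: n=50, 25 per arm, two-sided 0.05, uncorrected Pearson chi-square, prior-trial reductions of 40% (readmission) and 30% (missed appointments), and blocks of 3. Not in the documents: the control rate *p*. It is therefore varied, or solved for.

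**Formula.** With d = |p1 − p2| and pooled proportion p̄:

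s0 = √[p̄(1 − p̄)(1/n1 + 1/n2)], s1 = √[p1(1 − p1)/n1 + p2(1 − p2)/n2]

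Power = Φ[(d − 1.96·s0)/s1] + Φ[(−d − 1.96·s0)/s1]

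The second term is negligible for large gaps. Exact results enumerate all outcomes of the Pearson test.

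**Step 1: reproduce the 83%.** For 30% vs 70% at 25/25: p̄ = 0.50, s0 = √(0.25 × 2/25) = 0.1414, s1 = √(0.42/25) = 0.1296. Then (0.40 − 0.2772)/0.1296 = 0.948, and power = 82.8% (exact 85.9%). Over all absolute 40-point gaps this is the lowest value; 50% vs 10%, for example, gives 89.5%. The stated minimum is thus correct on the absolute scale. A 40% relative reduction does not have a minimum of 83%.

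**Step 2: compare the scales.** A 40-point reduction from control rate *p* is a relative reduction of 0.40/p. It is impossible below p = 40%, means no events in the digital arm at p = 40%, and equals a 40% relative reduction only at p = 100%.

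**Step 3: power for a 40% relative reduction at 25/25.**

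| Assumed control rate | Digital arm | s0 | s1 | Power |
|---|---|---|---|---|
| 20% | 12% | 0.1037 | 0.1031 | 12% |
| 30% | 18% | 0.1208 | 0.1196 | 17% |
| 50% | 30% | 0.1386 | 0.1356 | 30% |

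Solving for the control rate (exact test in brackets):

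- 40% reduction: 50% power at 69% (65%); 83% power at 90% (89%).
- 30% reduction: 83% power at 99% (96%).
- 65% reduction, the top of the 18-65% range read as relative: it equals 40 points at 0.40/0.65 = 61.5%, and reaches 83% power at 61% (59%).

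**Step 4: allocation.** Fifty patients make 16 blocks of 3 (48 patients) plus 2.

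- *Fixed 2:1.* 32/16 plus two more gives 33/17 or 34/16. Worst-case power over all 40-point gaps is 78.8% or 77.6% (exact 78.1% or 79.3%).
- *Blocks randomly 2:1 or 1:2.* One arm's size is 16 + Binomial(16, ½) + the first two places of a 17th block (2, 1 or 0, with probabilities 1/6, 4/6, 1/6). Exactly 25/25 occurs in 18.9% of sequences, and a split between 21/29 and 29/21 in 97.2%. Worst-case power is 82.8% at 26/24, 82.6% at 27/23 and 81.9% at 29/21. The loss is at most 82.8 − 81.9 = 0.9 points in that 97%.

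**The case against.** The plan has a fair defence. Aim 3 is a pilot about acceptability, feasibility and preliminary effectiveness. Section 4.4 disclaims power for small differences, and nowhere says the study is powered for the prior trial's effects. The sample-size sentence leads with the equipment limit and speaks of value *or* statistical significance. All of that stands, and it makes this a matter of wording rather than of design. It does not remove the problem: a 40% relative reduction is the earlier trial's readmission result and is not a small difference, so the caveat does not cover it, and the significance justification remains in the text.

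Four stronger readings are tempting, and the documents do not support them.

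- *The 40-point gap exceeds every effect cited.* It does not. The upper end of the 18-65% range, if relative, reaches 40 points at control rates of 61.5% or more; if absolute, it exceeds 40 points outright. That range names no outcome and concerns CHW care, so it does not rescue the sample-size sentence either.
- *The trial is underpowered at its actual rates.* No control rate is given for readmission or missed appointments, so this cannot be shown.
- *The 83% requires exactly 25/25.* It needs only near-equal arms, as the 26/24 and 27/23 results show. The fall below 80% depends on a fixed 2:1 block, which the plan neither states nor excludes.
- *The statement "Up to 20% of these readmissions" were potentially preventable sets a target effect.* It is a share of all adult readmissions nationally, not an intervention effect in heart failure.

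**Conclusion.** The point holds in limited form and is worth fixing. The 83% is arithmetically sound for an absolute 40-point gap in a binary endpoint with near-equal arms. It does not carry over to a 40% relative reduction, which has about 12% to 30% power at control rates of 20% to 50%, passes 50% power only at about 65-69%, and reaches 83% only at about 89-90%. The claim that 50 is the minimum for statistical significance is therefore unsupported for the prior trial's readmission and missed-appointment effects. Those effects are for CHW care, which both arms receive; no effect is cited for the digital addition. The power sentence does not address the Poisson comparison of ED visits.

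Blocks of 3 with two arms conflict with the planned 25/25 whatever the power consequence. That consequence is 4 to 5 points under a fixed 2:1 ratio (82.8 − 78.8 = 4.0; 82.8 − 77.6 = 5.2), and usually under 1 point if the ratio varies at random.

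Assumptions: the prior-trial percentages are relative, as their wording suggests; the control rates are illustrative; all 50 patients are analysed.

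**What to change.** 1. **Recruitment Procedures, remuneration, Aim 3.** Use an even block size, preferably varied (for example 2 and 4), so that 25/25 can be reached. If a block of 4 is cut short at patient 50, the worst split is 26/24, which still gives 82.8%. Otherwise, state the unequal ratio and restate the power.
2. **Research Design and Methods, Aim 3 sample size.** Delete the statistical-significance justification and let the resource limit stand as the basis for n=50.
3. **Section 4.4, Aim 3 power.** Replace the power sentence with:

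> With about 25 analysed per arm, a two-sided 0.05 chi-square test has about 83% power (normal approximation, worst case 30% vs 70%) for an absolute difference of 40 percentage points in a binary endpoint (30-day readmission or missed appointments). A reduction of this size requires a control proportion of at least 40% and is larger than the relative reductions in readmission and missed appointments reported in the prior CHW trial. The figure does not apply to ED visit counts. A non-significant effectiveness result will not be read as absence of effect.

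The cost is three text edits and, if allocation has already been generated, a check of the list. No patients are added and the planned tests are unchanged. The plan gives up only the claim that 50 was chosen to reach significance on effectiveness.
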